#### 1 INTRODUCTION

This document is a clinical investigational plan for a human research study. The study will be conducted in accordance with the ethical principles that have their origin in the Declaration of Helsinki. By participating in the study, the Investigator agrees to adhere to all stipulations of this protocol, the conditions of IRB approval, federal and local regulatory requirements, 21CFR 812, ISO-14155 and International Conference on Harmonization Good Clinical Practice guidance ICH GCP.

#### 1.1 Background and Rationale

Masimo Corporation is the developer of noninvasive technologies for the measurement and monitoring of physiological variables, such as arterial oxygen saturation (SpO2), total hemoglobin concentration (SpHb), carboxyhemoglobin concentration (SpCO), methemoglobin concentration (SpMet), acoustic respiration rate monitoring (RAM), and cerebral and regional oximetry (rSO2, O3TM). These technologies are noninvasive and have a good patient safety record.

A continuous supply of oxygen is essential for normal cell function. Failure of a patient's oxygen supply to meet metabolic needs is common to all forms of circulatory failure, tissue acidosis, and ultimately mortality. Like all essential commodities for body functions, optimal quantities of oxygen are required. A patient's oxygen status can be largely classified into 3 ranges: Hypoxia (less than normal), Normoxia (normal) and Hyperoxia (more than normal). The three states are typically classified using dissolved oxygen levels in the plasma (PaO2), instead of arterial hemoglobin oxygen saturation (SaO2), due to sensitivity of PaO2 in all three states including hyperoxia (unlike SaO2). Figure 1 shows the three oxygen states based on PaO2 values along with the relationship between PaO2 and SaO2.

# OxyHemoglobin Dissociation Curve

[figure not shown]

Figure 1: The oxygen dissociation curve with the three oxygen states

In order to prevent episodes of hypoxia, patients in critical care are administered a certain amount of supplemental oxygen to prevent hypoxia and improve safety in situations where the oxygen supply may be lost intermittently. However this excess supply should be in moderation as large amounts of oxygen may result in lung damage or other complications. Hence it becomes imperative to monitor the amount of surplus oxygen in blood.

Currently, clinicians monitor a patient's oxygen status, both continuously and non-invasively, using a pulse oximeter to obtain SpO2 (a proxy for SaO2) levels. However, SpO2 is sensitive in the normoxic and hypoxic regions and largely remains flat in the hyperoxic region (Figure 1). Clinicians consequently must resort to invasive blood sampling to obtain PaO2 values for oxygen status within the hyperoxic zone. This method has multiple drawbacks such as limited information from

intermittent sampling to potential delay due to the time difference between blood draw and when the PaO2 value is obtained through blood gas machines, and potentially significant loss of blood due to multiple blood draws.

The Oxygen Reserve Index (ORi) is a reference that could help clinicians with their assessments of normoxic and hyperoxic states by scaling the measured absorption information between 0.00 and 1.00.

While not a direct measurement of PaO2, ORi provides a continuous and non-invasive index which correlates with changes in PaO2 values in the range of 100 to 200mmHg.

ORi together with pulse oximetry may provide useful reference information about a patient's partial pressure of oxygen in arterial blood (PaO2) and the transition between oxygen regions such as moving from normoxic to hypoxic regions. This can be useful during clinical applications such as during endotracheal intubation, in which unintended desaturations may occur. Additionally, ORi may be used as reference information for clinicians when they monitor the patient's reserve oxygen supply.

[figure not shown]

Figure 2: PaO2 vs SaO2 and SvO2

This protocol is designed to evaluate the correlations between  $\Delta ORi$  and  $\Delta PaO2$  and the potential use of ORi as an early warning of impending arterial oxygen desaturation.

# 2 STUDY OBJECTIVES

#### 2.1 Specific aims:

- evaluate the clinical utility of the change in the Oxygen Reserve Index as an early warning of impending arterial oxygen desaturation in adult patients
- characterize the correlations between the Oxygen Reserve Index and the arterial oxygen content during preoxygenation and induction of general anesthesia in adult patients

# 2.2 Hypothesis (constructed as the null):

Intraoperative changes in ORi will not correlate with increases in arterial oxygen content during pre-oxygenation or induction of general anesthesia and ORi will not provide clinically significant additional warning of impending arterial desaturation.

#### 3 STUDY DESIGN

This is a prospective, non-blinded, non-randomized study of the Oxygen Reserve Index (ORi) in a clinical setting. It is designed to evaluate the correlations with ORi and  $\Delta$ PaO2 and the potential use of ORI as an early warning of impending arterial oxygen desaturation.

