#### 6 STUDY DEVICE

#### 6.1 **Study Device**

The Masimo Radical-7 is a noninvasive monitor that measures arterial oxygen saturation (SpO2), pulse rate (PR), and perfusion index (PI), along with optional measurements of hemoglobin (SpHb), carboxyhemoglobin (SpCO®), total oxygen

content (SpOC), methemoglobin (SpMet), Pleth Variability Index (PVI®), Oxygen Reserve Index (ORI™), Acoustic Respiration Rate (RRa®), and Pleth Respiration Rate (RRp). Masimo SET® technology is clinically proven to satisfy all sensitivity and specificity requirements for pulse oximetry. Masimo rainbow® technology uses 7+ wavelengths of light to continuously and noninvasively measure carboxyhemoglobin (SpCO), methemoglobin (SpMet), and total hemoglobin (SpHb®), as well as providing a more reliable probe-off detection. Total oxygen content (SpOC) provides a calculated measurement of the amount of oxygen in arterial blood, which may provide useful information about oxygen both dissolved in plasma and combined with hemoglobin. Perfusion Index (PI) with trending capability indicates arterial pulse signal strength and may be used as a diagnostic tool during low perfusion. Pleth Variability Index (PVI) may show changes that reflect physiologic factors such as vascular tone, circulating blood volume, and intrathoracic pressure excursions. [The utility of PVI is unknown at this time and requires further clinical studies. Technical factors that may affect PVI include probe malposition and patient motion.] Oxygen Reserve Index (ORI) is an index measured noninvasively and continuously to provide an earlier indication of impending hypoxia by extending oxygen monitoring of pulse-oximetry to the moderate hyperoxic regions. Respiration rate can be determined by the acoustic (RRa) or plethysmographic waveform (RRp). Signal IQ is a feature for signal identification and quality indication during excessive motion and low signal to noise situations. FastSat® tracks rapid changes in arterial O2. A detailed description of the Masimo Radical-7 can be found in the attached manual.

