The Masimo Root System is also being used in this study. The Root System is indicated for use by healthcare professionals for the monitoring of multiple physiological parameters in healthcare environments. The Root works together with the Radical-7 to display data. The Root serves as a convenient alternative user interface to integrate modules to provide health care professionals the ability to access, control and monitor measurement technologies (within the respective modules) that have been previously cleared by the FDA.

Rainbow Adhesive Sensors are FDA cleared for the measurement of functional oxygen saturation of arterial hemoglobin (SpO2), pulse rate (PR), perfusion index (PI), pleth variability index (PVI), carboxyhemoglobin saturation (SpCO), methemoglobin saturation (SpMet), total hemoglobin (SpHb) and total oxygen content (SpOC). Although no modifications are required for the Rainbow Adhesive sensors for the study, the sensors have not been cleared for the indications for use of measuring ORi.

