### 7 STUDY PROCEDURES

- 7.1 Following arrival of the patient in the operating room all standard and planned physiological monitors will be placed. A baseline ORi will be measured and an arterial blood gas (ABG) sample will be collected for measurement of the PaO2.
- 7.2 As per routine, the patient will then be pre-oxygenated with 100% oxygen. a second ORI will be recorded and ABG sample collected.
- 7.3 General anesthesia will be induced with a combination of amnestics, narcotics, intravenous induction agents and muscle relaxants as clinically indicated. With stable mask ventilation, a third ORI will be recorded and ABG sample collected immediately prior to initiating laryngoscopy and endotracheal intubation.
- 7.4 Intubation will be under direct visualization using a GlideScope. When the arterial hemoglobin saturation reaches fourth ORi will be recorded, an ABG sample will be collected and ventilation will be initiated with 100% oxygen either via the endotracheal tube or resumed mask ventilation.
- 7.5 A final post-induction ORi measurement and ABG sampling will occur 5 minutes following initiation of controlled ventilation with 100% oxygen.

This planned protocol sequence can be summarized graphically as:

Arterial blood gas measurement: ABG samples will be analyzed using Radiometer's ABL blood gas analysis system. Each sample will use of blood for a total blood volume of for this study.

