# 11.4 Data Transfer and Storage

The information will be stored in a password protected electronic database at the study site. Device data along with an electronic copy of the CRF will periodically be securely uploaded to sponsor via secure FTP portal. Only authorized sponsor personnel will have access to the transferred data, and will move it to a secure and backed-up drive at Masimo. CRFs will be checked for accuracy and completeness of data. If there are inconsistent or missing data points, a data query list will be generated and submitted to the PI or designee, who shall both follow GDP practices for data correction by striking through the old entry, adding in new entry with initial and date, and resend to Masimo the corrected CRF. Once all queries

have been resolved, Masimo engineers are notified that data is ready for analysis. To ensure data integrity, Masimo engineers will only have read access to study data, therefore are unable to unintentionally tamper with the original data files.

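### ORi is not masked from the anesthesia team, and the samples at the end of pre-oxygenation and before laryngoscopy have no visible timing rule independent of ORi

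*Combined protocol and SAP*

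**What the plan says.** Section 3 sets the design: "This is a prospective, non-blinded, non-randomized study of the Oxygen Reserve Index (ORi) in a clinical setting". Section 6.1 says of the index under test: "Oxygen Reserve Index (ORI) is an index measured noninvasively and continuously". It adds of the two bedside devices: "The Root works together with the Radical-7 to display data". It does not say which parameters are shown, on which screen, or to whom. It also notes that "the sensors have not been cleared for the indications for use of measuring ORi". Section 6.2 describes the study as observation with recording of ORi and blood gases, but no section forbids using ORi in care or in choosing when to sample.

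Section 7 plans five paired ORi and blood gas readings. They are timed as follows:

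- **Sample 1 (7.1):** baseline, before pre-oxygenation.
- **Sample 2 (7.2):** "As per routine, the patient will then be pre-oxygenated with 100% oxygen", after which "a second ORI will be recorded and ABG sample collected". The readable text gives no duration or end rule.
- **Sample 3 (7.3):** "With stable mask ventilation, a third ORI will be recorded and ABG sample collected immediately prior to initiating laryngoscopy and endotracheal intubation".
- **Sample 4 and start of ventilation (7.4):** tied to a value of arterial saturation, which is missing from the public text.
- **Sample 5 (7.5):** 5 minutes after controlled ventilation begins.

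Section 8.2 requires sensitivity above 85% and specificity above 80% for ΔPaO2 against ΔORi. Section 8.3 takes the end of pre-oxygenation as the reference time for sensitivity and baseline as the reference time for specificity.

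**The concern.** When an index is judged against a reference measurement, the moment of measurement should not depend on the index. Samples 2 and 3 are left to clinical judgement, in a study where the index may be in view of the people making that judgement.

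Two routes follow. First, the team could draw sample 2 when ORi is visibly high. Every later change counted towards sensitivity is measured from that sample, so a chance high reading makes a later fall in ORi more likely whatever PaO2 does. Second, a team watching ORi might start laryngoscopy earlier or later than it otherwise would. That alters the course of the apnea period on which the secondary, early-warning endpoint depends.

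Influence on the team is plausible. Section 1.1 itself presents ORi as potentially useful to clinicians around intubation. At stake is whether a sensitivity above 85% could be read as the index's own performance.

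**Working it through.** **Is there a plan figure to reproduce?** Not for this point. The only computed figure in the plan is the minimum of 22 subjects (section 8.1). It is carried over from a healthy-subject calculation whose inputs are not given, and nothing below depends on its derivation.

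**Step 1: which times could ORi influence?**

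| Event | Timing rule in readable text | Open to ORi if visible? |
|---|---|---|
| Sample 1 | Baseline, before pre-oxygenation | Little scope |
| Sample 2 | After routine pre-oxygenation | Yes |
| Sample 3 | Stable mask ventilation, just before laryngoscopy | Yes |
| Sample 4, start of ventilation | Saturation trigger | Not directly |
| Sample 5 | 5 minutes after controlled ventilation starts | No |

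**Step 2: does an open time feed an acceptance criterion?** Yes. Under section 8.3, sensitivity is N3/(N2 + N3) with sample 2 as reference. Section 8.2 describes the reference time differently, as the sample nearest a PaO2 threshold; I follow 8.3 because it is tied to the formula. Specificity uses baseline, so its reference is not exposed in the same way. Figure 3 is not available, so the exact cells cannot be checked.

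**Step 3: could timing on ORi matter numerically?** This is an illustration, not an estimate. All its inputs are assumed:

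- PaO2 truly falls after sample 2.
- ORi at sample 2 is a level plus normal noise with standard deviation σ, and the later ORi has the same noise around a level lower by d.
- A pair counts as correct if ORi falls.
- The team either takes sample 2 at an arbitrary moment or at the highest of six independent displayed readings.

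For an arbitrary moment, apparent sensitivity is Φ(d/(σ√2)). With σ = 0.10 and d = 0.05 this is Φ(0.354) = 0.638. With d = 0.10 it is Φ(0.707), about 0.76. The highest-of-six case was simulated with 200,000 draws.

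| σ | d | Arbitrary time | Highest of six |
|---|---|---|---|
| 0.05 | 0.05 | 0.760 | 0.973 |
| 0.05 | 0.10 | 0.922 | 0.997 |
| 0.10 | 0.05 | 0.638 | 0.933 |
| 0.10 | 0.10 | 0.761 | 0.973 |
| 0.20 | 0.05 | 0.569 | 0.900 |
| 0.20 | 0.10 | 0.639 | 0.934 |

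A limiting case needs no value of σ. If ORi carries no information (d = 0), the six candidate readings and the later one are exchangeable. The later one is the largest with probability 1/7, so apparent sensitivity is 1 − 1/7 = 6/7 = 0.857, against 0.50 at an arbitrary moment. Extreme timing on the index could thus pass an 85% criterion with no true signal.

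**Step 4: scale.** With 22 subjects and one independent pair each, the 95% Wald half-width at 0.85 is 1.96 × √(0.85 × 0.15/22) = 0.149. At σ = 0.10 the illustrated shifts are 0.933 − 0.638 = 0.295 and 0.973 − 0.761 = 0.212, both larger.

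Picking the exact peak of six independent readings is a worst case. Smoothed or correlated readings, or an index at the top of its 0.00–1.00 scale, would reduce the effect.

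**The case against.** The strongest reply is that display to the treating team is inferred. The sentence on the Root is a general device description, and non-blinded does not by itself say who looks at ORi. Section 6.2 points towards passive recording. This stands: the accurate statement is that the plan does not say who sees ORi, and nothing masks it.

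Second, the timing gap may be partly an artefact of the public text. Step 7.4 has visible removals, and the graphic announced at the end of section 7 is missing and might hold times. This also stands, which is why the point is limited to the readable text. A timing rule in the graphic would narrow it.

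Third, PaO2 comes from a blood gas analyser. ORi cannot change that reading, but it could still change when the sample is drawn.

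A reader might go further and infer that clinicians seeing ORi fall would ventilate before desaturation, so that true warnings vanish or appear as false alarms. The documents do not support this. Step 7.4 ties ventilation to saturation, so ventilating on ORi would depart from the protocol. Section 9.4 requires prior approval of deviations, with an emergency exception, and reporting of unapproved ones that may affect scientific soundness. Nor can that effect be sized by treating 85% as a rate of warnings per subject. In section 8.2 it is a criterion for paired changes in PaO2 and ORi, and the readable plan defines neither a warning threshold nor a false-alarm count.

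**Conclusion.** The concern holds in a limited form. A stated design feature, together with unspecified timing of samples 2 and 3, lets the index under test influence its own sensitivity reference and the start of laryngoscopy. It does not extend to sample 4, the start of ventilation or sample 5.

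The size is unknown. The figures above show only that ORi-guided timing, if it occurred, could move sensitivity across 85%. They rest on assumed noise, an assumed true fall and a deliberately extreme selection rule. A reader might infer that the results could not be read as ORi's performance at all. That goes too far, because the documents do not show that any sample is timed on ORi. The plan simply does not prevent or record it. This is a cheap improvement to a stated design choice and does not by itself invalidate the study.

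**What to change.** In section 3, state: *open-label, with the treating team masked to ORi from the baseline sample to the fifth sample.*

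In section 7, add: *SpO2 and all standard monitors remain displayed to the treating team. The time of each blood sample is set without reference to ORi. The ORi value paired with each sample is taken from the stored device record at the time-stamp of that blood gas.*

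Both parts are needed, because masking alone leaves samples 2 and 3 without a stated timing rule. If ORi cannot be masked, state who sees it and log on the case report form any use of it in timing a sample or starting laryngoscopy. No change to clinical care is proposed.

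The cost is small: a display change and a few sentences. Data transfer already exists, since section 11.4 says "Device data along with an electronic copy of the CRF will periodically be securely uploaded to sponsor". The downside is that the treating team loses the bedside ORi reading. The fix assumes that the monitor can hide ORi while showing SpO2, and that it stores ORi with times. Neither is stated in the protocol, so both should be checked in the device manual first.

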# 3.1 Study Endpoints

This is a prospective clinical study designed with the following endpoints:

- Primary endpoint measure the ΔPaO2and it's correlation with changes in ORi (ΔORi) during the
  induction of general anesthesia in patients in whom continuous arterial pressure monitoring is a planned
  component of the anesthetic monitoring.
- Secondary endpoint evaluate the potential clinical utility of the ORi as an early warning for impending desaturation.

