# 8.2 Acceptance criteria

In accordance with ISO-80601-2-61, SpO2 accuracy is determined as accuracy root mean square (ARMS), where SpO2 measurements are compared with reference SaO2 measurements. However unlike SpO2, ORi is an index value without a unit and ORi does not directly measure PaO2. Therefore, sensitivity and specificity analysis is used to evaluate ORI's performance relative to the changes in PaO2.

Although concordance calculation is based on sensitivity and specificity analysis, concordance analysis is not applicable for the sick subjects because of the lack of sample size. Thus the specifications for ORI are the following:

- Specificity of ΔPaO2 vs. ΔORI > 80%
- Sensitivity of  $\triangle PaO2$  vs.  $\triangle ORI > 85\%$
- Concordance of ΔPaO2 vs. ΔORI > 80%

Where  $\Delta$ PaO2 is the change in PaO2 and  $\Delta$ ORi is the change in ORi. These specifications are based on the study by Applegate et al. The Applegate study evaluated the ORI to PaO2 relationship during surgery of 106 patients. The data showed that decreasing ORI had 77.7% sensitivity and 76.7% specificity for detecting decreasing PaO2.

In determining specificity and sensitivity,  $\Delta PaO_2$  and  $\Delta ORi$  are defined as:

$$\Delta PaO_2 = PaO_2(t) - PaO_2(t_{ref})$$

$$\Delta ORI = ORI(t) - ORI(t_{ref})$$

Where  $t_{ref}$  is the time of the sample closest to  $PaO_{2threshold}$  in a mmHg window. Thus, a mmHg window is used as it is not possible to draw a blood sample at the exact value of  $PaO_{2threshold}$ .

Samples with  $\triangle$  PaO2 of mmHg are ignored.

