# 8.3 Statistical analysis

Similar statistical analysis as described in the study with healthy subjects ( will be performed on the data for this study with sick subjects. However unlike healthy subjects, the FiO2 levels for sick subjects cannot be easily varied. Therefore, substantially fewer PaO2 samples are available for sick subjects. As a result, all PaO2 samples for sick subjects are accounted for in data analysis even if the PaO2 sample is outside the 100 to 200 mmHg range.

[figure not shown]

Figure 3: Specificity and Sensitivity Illustration for ΔPaO2 vs ΔORi

In accordance with Figure 3, the following relationships are defined as:

Specificity =  $\frac{N1}{(N1 + N4)}$ , where  $t_{ref}$  is the baseline sample time

Sensitivity =  $\frac{N3}{(N2 + N3)}$ , where  $t_{ref}$  is the sample time at the end of 100% pre-oxygenation.

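### Section 8 as supplied tests direction of change only: it gives no correlation estimate for the primary endpoint and no measure of warning beyond SpO2 for the secondary

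*Combined protocol and SAP*

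**What the plan says.** Section 3.1 defines the primary endpoint as the change in PaO2 and "it's correlation with changes in ORi" during induction. The secondary endpoint is the potential use of ORi as an early warning. Sections 2.1 and 3 repeat both aims. The null in Section 2.2 has two parts: no correlation, and no additional warning of a clinically significant size.

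Section 8.2 says that "sensitivity and specificity analysis is used to evaluate" ORi against changes in PaO2, on the ground that "ORi is an index value without a unit and ORi does not directly measure PaO2". The limits are specificity above 80% and sensitivity above 85%. A concordance limit above 80% is also listed, although the same section calls concordance not applicable in these subjects.

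Section 8.3 defines specificity as N1/(N1+N4), where the reference time "is the baseline sample time", and sensitivity as N3/(N2+N3), where it "is the sample time at the end of 100% pre-oxygenation". It opens with "Similar statistical analysis as described in the study with healthy subjects", and the reference that follows is cut off. Because "substantially fewer PaO2 samples are available for sick subjects", it keeps every PaO2 sample "even if the PaO2 sample is outside the 100 to 200 mmHg range". Figure 3, which defines the N counts, is not shown.

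**The concern.** The endpoints ask how closely ORi changes follow PaO2 changes, and how much earlier ORi warns than the monitor already in use. The visible analysis asks whether the two changes go in the same direction. It names no correlation coefficient, no interval for one and no way of handling repeated samples within a subject. It also names no ORi event, no time to an SpO2 event and no amount of lead that would count as clinically significant. SpO2 appears in Section 8 only in the remark on oximeter accuracy.

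If Section 8 is followed as it stands, the primary endpoint is judged on direction alone. If a correlation is added after the data are seen, its value depends heavily on whether rises and falls are pooled. The early-warning endpoint would have a direction result but nothing to set against the word additional in Section 2.2.

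**Working it through.** **1. The plan's own figure.** The minimum of 22 subjects (Sections 5.1 and 8.1) cannot be reproduced, because no effect size, power or half-width is given. It does not reveal which analysis was intended either. With assumed inputs:
- A proportion of 0.85 with half-width 0.15 gives n = 1.96² × 0.85 × 0.15 / 0.15² = 21.8, so 22.
- A correlation tested at two-sided 5% with 80% power, n = ((1.96 + 0.842)/atanh r)² + 3, gives 24 for r = 0.55 and 20 for r = 0.60.

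**2. What direction says about correlation.** If the changes are zero-mean bivariate normal, agreement in sign is 1/2 + arcsin(r)/π. That is 67%, 75%, 80% and 86% for r = 0.5, 0.7, 0.8 and 0.9, so direction carries some information. It does not fix r. In simulations with 100% sign agreement, the overall r was 1.00, 0.78 or 0.30, depending only on how the sizes of change were related. Among rises alone it was 1.00, 0.00 and 0.00.

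**3. Effect of pooling.** The ranges are assumed: change in PaO2 50 to 350 mmHg, change in ORi 0.1 to 0.9, direction always right, sizes unrelated, 22 subjects.
- Rise phase alone: mean rank correlation 0.00, with 95% of runs from about -0.43 to 0.43.
- 22 rises with 22 falls: Pearson 0.84, rank 0.75. The Pearson value can be checked by hand. The means are 200 and 0.5, and the variances are 300²/12 = 7,500 and 0.8²/12 = 0.0533. So r = (200 × 0.5)/√((200² + 7,500)(0.5² + 0.0533)) = 100/120.0 = 0.83.
- Within-subject correlation over the five samples: 0.68 (0.56 to 0.78).

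The scheduled oxygen steps alone can therefore produce a large pooled coefficient.

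**4. Effect of the bounds.** Section 1.1 scales ORi from 0 to 1 and ties it to PaO2 of 100 to 200 mmHg. Take ORi as (PaO2 − 100)/100 plus noise of SD 0.08, capped at 0 and 1. This index tracks PaO2 by construction. The baseline and pre-oxygenated PaO2 ranges are assumed, and the fall ends at 60 to 110 mmHg.

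| Baseline, pre-oxygenated PaO2 (mmHg) | Rank r, rise / fall | ORi rise exactly 1 |
|---|---|---|
| 70–110, 250–450 | 0.12 / 0.14 | 74% |
| 70–130, 250–450 | 0.23 / 0.14 | 50% |
| 60–100, 120–450 | 0.68 / 0.64 | 70% |
| 60–100, 110–250 | 0.91 / 0.91 | 33% |

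A rule requiring both lower 95% limits to exceed 0 is met in under 2% of runs in each of the first two rows.

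**5. Precision.** For a rank correlation of 0.5 with one pair per subject, SE on the Fisher scale is √((1 + r²/2)/(n − 3)).
- n = 22: √(1.125/19) = 0.243, and atanh 0.5 = 0.549. The limits are tanh(0.072) = 0.07 and tanh(1.026) = 0.77.
- n = 100 (the enrolment maximum): 0.33 to 0.64.

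**6. Who is counted for lead time.** If lead were normal with mean 30 s and SD 40 s (assumed), Φ(−0.75) = 23% of subjects would have none. The median is 30 s with everyone included and 41.5 s if those subjects are dropped.

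**The case against.** The strongest reply is that the plan may already contain what seems to be absent. Section 8.3 relies on a healthy-subject analysis whose reference is cut off, and Figure 3 is missing. That stands. A reader might infer that the study has no analysis of its primary endpoint, and the documents do not support that. If the borrowed analysis has a correlation and a lead time, the gap is only that 8.3 does not state them. The description is merely similar, however, and 8.3 departs from it on which samples are kept, so they should still be written down for this population.

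A second reply is that Section 8.2 explains its choice, and that sensitivity and specificity are how the plan makes a loosely worded correlation operational. This stands in part. Sensitivity referenced to the end of pre-oxygenation also bears on warning, since Section 1.1 says SpO2 is insensitive to hyperoxia. It would be wrong to call these measures irrelevant. But the stated reason, that ORi has no unit and is not a direct PaO2 measurement, rules out an accuracy statistic and not a correlation, which needs no common unit. If the measures are meant as a replacement, Section 3.1 should say so.

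Third, all the magnitudes above are assumed, and wholly unrelated sizes are an extreme case. That is correct. The mismatch itself does not depend on them.

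**Conclusion.** The point holds for the supplied text and is worth fixing. Following visible Section 8 leaves both stated questions without a direct answer. Meeting the 80% and 85% limits would be indirect evidence that ORi moves with PaO2, but would give neither a correlation nor an amount of warning beyond SpO2.

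On the assumed ranges, pooling alone moves the rank correlation from about 0 to about 0.75. That is why the coefficient must be fixed before the data are seen; it is not a forecast of this study's result.

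A reader might also infer that the phase-specific correlations should become a pass/fail test. The working argues against it: an index that tracks PaO2 but sits at its bounds would almost never pass. Confidence is medium, because the borrowed analysis cannot be seen.

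**What to change.** **Primary endpoint, Section 8.3.**
- Pre-specify rank correlations of change in ORi with change in PaO2, each with a 95% confidence interval. Give one for the rise (baseline to end of pre-oxygenation) and one for the fall (end of pre-oxygenation to the fourth sample). Present them as estimates.
- Report how many subjects have ORi at 0 or 1 at each sample. Give a pooled within-subject correlation as supportive only.
- State which reference time applies: 8.2 uses the sample nearest a PaO2 threshold, while 8.3 uses two fixed times. State whether the exclusion in 8.2 of samples by size of PaO2 change applies to the correlation, given that 8.3 keeps all samples. Note that the rise comes before induction (7.1 and 7.2, against 7.3), whereas Section 3.1 places the endpoint during induction.
- Keep sensitivity and specificity as acceptance measures. If they are meant to replace correlation, reword Section 3.1. If the healthy-subject analysis already has a correlation, write it into 8.3.

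**Secondary endpoint.** If the oximeter recordings (Sections 11.1 and 11.4) are time-stamped, add a per-subject lead time from a pre-specified ORi fall to a pre-specified first fall in SpO2. Include all subjects, count no earlier ORi fall as no lead, and give the median with a 95% confidence interval. The investigators should state in advance what lead is clinically significant. Time to the saturation point in 7.4 may be reported as well. It cannot stand in for additional warning, because it includes time when SpO2 is already falling.

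**Wording.** Reconcile arterial oxygen content (Sections 2.1 and 2.2) with PaO2 (Sections 3.1 and 8.2). Section 6.1 describes content as dissolved plus haemoglobin-bound oxygen, so the terms are not interchangeable.

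**Cost.** Wording and a little analysis, with no new subjects, samples or devices. The downsides are wide intervals at 22 subjects, coefficients that can be low because ORi is at its bounds, and a lead time that depends on time-stamps the documents do not confirm.
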